### **7.3.3 Safety analyses**

The analysis and reporting of adverse events will concentrate on treatment-emergent adverse events. To this end, all adverse events occurring between first drug intakes until 7 days after last treatment administration will be considered ‘treatment-emergent’. Adverse events that start before first drug intake and deteriorate under treatment will also be considered as ‘treatment-emergent’.

AEs will be coded using lowest level terms of the Medical Dictionary for Drug Regulatory Activities (MedDRA). AEs occurring in routine medical practice will be evaluated. The relationship of an AE to JARDIANCE® Tablets will be assessed by the investigator and the sponsor. An ADR is defined as an AE if either the investigator or the sponsor (or both) assess the causal relationship of JARDIANCE® Tablets either as “Possibility high”, “Possibility low” or “Unknown”.

The frequency of ADRs will be tabulated by system organ class and preferred term according to the current MedDRA version. The frequency of SAE will also be tabulated likewise.

The incidence of ADRs stratified based on patient demographics will also be investigated.

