## **2. RATIONALE, OBJECTIVES, AND BENEFIT-RISK ASSESSMENT**

### **2.1 RATIONALE FOR PERFORMING THE STUDY**

In Japan, post-approval execution of post marketing surveillance (PMS) is requested by the Japanese Pharmaceutical Affairs Law (J-PAL) in order to accumulate safety and efficacy data for re-examination. Re-examination period is defined by J-PAL. New integrant is 8 years for re-examination. Eight years after approval of a new substance, results of PMS need to be submitted as a part of re-examination dossier to the Japanese regulatory authority, the Ministry of Health, Labour and Welfare (MHLW).

Collected data from PMS will be included in the Japanese periodic safety reports and submitted to MHLW on designated dates until the end of re-examination period.

The protocol may be revised because of new information or knowledge obtained in the course of conducting PMS. When a change of the approved label such as in dosage and administration or indications is made during the re-examination period of JARDIANCE® Tablets (except that for this change a re-examination period is newly designated by MHLW) and NBI finds it necessary to revise this protocol, handling each matter should be discussed and the protocol may be revised. If any issue or concern arises (e.g. suggestion of a potential for clinically significant adverse reaction, remarkable increase in incidence of an adverse reaction, or any issue or concern on safety or efficacy assessment made prior to the approval of JARDIANCE® Tablets) in the course of PMS, implementation of additional special surveillance or post-marketing clinical trial should be discussed to identify or confirm a cause or estimated cause of such issue. Special surveillance is defined by J-PAL. It means surveillance for long-term use or special patient population (elderly, renal/hepatic dysfunction etc.).

SGLT-2 inhibitor is a drug class with a new mode of action, and does not comprise sufficient Japanese safety data within the class. It's not that there is a particular safety issue concerning JARDIANCE®; however, further surveillance is needed to monitor possible increase in the incidence of malignant tumor which is potentially associated with drugs of the same class, as well as the effect on kidneys attributable to its mode of action by which a long-term use stimulates the urinary excretion of glucose, and also the effect on hepatic function and bone metabolism.

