#### Serious adverse event

A serious adverse event is defined as any AE which

- results in death,
- is life-threatening,
- requires in-patient hospitalization, or
- prolongation of existing hospitalisation,
- results in persistent or significant disability or incapacity, or
- is a congenital anomaly/birth defect

Life-threatening in this context refers to a reaction in which the patient was at risk of death at the time of the reaction; it does not refer to a reaction that hypothetically might have caused death if more severe.

Medical and scientific judgment should be exercised in deciding whether other situations should be considered serious reactions, such as important medical events that might not be immediately life threatening or result in death or hospitalisation but might jeopardise the patient or might require intervention to prevent one of the other outcomes listed above. Examples of such events are intensive treatment in an emergency room or at home for allergic bronchospasm, blood dyscrasias or convulsions that do not result in hospitalisation or development of dependency or abuse. Any suspected transmission via a medicinal product of an infectious agent is also considered a serious adverse reaction.

An AE which possibly leads to disability will be reported as an SAE. Every new occurrence of cancer or an exacerbation of an existing cancer will be reported as a SAE regardless of the duration between discontinuation of the drug and the occurrence of the cancer.

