#### Collection of AEs

The study design is of non-interventional nature and the study is conducted within the conditions of the approved marketing authorisation. Sufficient data from controlled interventional trials are available to support the evidence on the safety and efficacy of the studied BI drug. For this reason the following AE collection and reporting requirements have been defined.

The following must be collected by the investigator in the (e)CRF from first intake of JARDIANCE® Tablets at baseline visit and within 7 days (inclusive) after the last intake:

- all ADRs (serious and non-serious) as soon as possible,
- all AEs with fatal outcome in patients exposed to JARDIANCE® Tablets as soon as possible,

All ADRs, including those persisting after study completion must be followed up until they are resolved, have been sufficiently characterized, or no further information can be obtained.

The investigator carefully assesses whether an AE constitutes an ADR using the information below.

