6. GENERAL ANALYSIS DEFINITIONS

6.1 TREATMENT(S)

For basic study information on treatments, please refer to NIS Protocol Section 4. The technical specification for treatment set-up is described in the analysis data set (ADS) plan. For efficacy analyses, data up to 7 days after last treatment intake will be considered as on treatment for HbA1c and 1 day for FPG. For safety analyses, data up to 7 days after last treatment intake will be considered as on treatment for AE, 1 day for weight, blood pressure and pulse and 3 days for laboratory measurements.

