AE analyses will be carried out after integrating AE data from CRF and AE data from Local PV safety database (Perceive).

[figure not shown]
In addition, events coded as “no adverse event”, etc. will not be included in the AE analyses. The list of codes will be provided by Drug Safety.

[figure not shown]
Priority survey items, Important identified risk, Important potential risks and Significant ADRs

The following AEs are summarised on the basis of the Standardised MedDRA queries (SMQs) or Boehringer Ingelheim customised MedDRA query (BICMQ) by primary SOC and PT.

*:1 ADRs are also summarised.

*2: ADRs occurred in summer (the onset date is in June, July, August, or September) are also summarized.

Risk ratios with 95% confidence intervals will be shown for subgroup analyses. In case that there will be the significant difference between each factor, the frequency of patients with drug related AEs (ADRs) and with serious AEs will be summarized by primary SOC and PT. Due to the high number of exploratory subgroup analyses, it is recognised that the likelihood of chance findings is high and therefore subgroup results should be interpreted with caution.

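### Cancers starting more than 7 days after last intake must be reported, but the readable analysis rules give them no place in the adverse-event tables

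*Protocol*

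**What the plan says.** Protocol 2.1 says there is no particular safety issue with the product, but gives as one reason for the surveillance to "monitor possible increase in the incidence of malignant tumor which is potentially associated with drugs of the same class". Under Serious adverse event, Protocol 5.2.2.1 sets a rule for cancer alone: every new or worsened cancer "will be reported as a SAE regardless of the duration between discontinuation of the drug and the occurrence of the cancer".

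The analysis sections use a different clock. Protocol 7.3.3 states that "The analysis and reporting of adverse events will concentrate on treatment-emergent adverse events", and defines these by the rule that "all adverse events occurring between first drug intakes until 7 days after last treatment administration will be considered" treatment-emergent. SAP 6.1 agrees: "For safety analyses, data up to 7 days after last treatment intake will be considered as on treatment for AE". SAP section 4 declares no change from the protocol's methods.

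SAP 7.8.1 merges adverse events from the CRF with those in the local safety database. It summarises the priority items and risks by standardised or "customised MedDRA query (BICMQ) by primary SOC and PT". The list of those items is not readable.

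On collection, Protocol 5.3.1 requires adverse drug reactions and fatal events in the eCRF from first intake "and within 7 days (inclusive) after the last intake". Protocol 6.1 ends observation at 156 weeks or at the last visit before discontinuation.

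**The concern.** Cancer is the one class of event that the protocol frees from any time limit for reporting, and it is a stated reason for the study. A 7-day tail suits acute reactions; it does not suit an outcome that can appear long after exposure. If the tail governs the tables, cancers that sites reported as instructed drop out at the analysis stage, and the reader of the report is not told how many. The count on one of the study's named safety questions would then be smaller than the count in the sponsor's own database.

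**Working it through.** **The plan's own figure.** Protocol 7.6 says that with 3,000 completers an ADR of true incidence 0.10% (0.16%) is seen at least once with probability 95% (99%). With P = 1 − (1 − p)^3000:

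- p = 0.0010: P = 95.03%
- p = 0.0016: P = 99.18%

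Both figures reproduce. They concern seeing at least one event and have no bearing on whether all reported cancers are counted.

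**The rules side by side.**

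| Step | Section | Limit after last intake | Readable exception for cancer |
|---|---|---|---|
| Reporting as SAE | Protocol 5.2.2.1 | None | The rule is specific to cancer |
| eCRF collection | Protocol 5.3.1 | 7 days; ADRs and fatal events | None |
| Expedited reporting | Protocol 5.3.1 | 7 days; ADRs, fatal events, pregnancy forms | None |
| End of observation | Protocol 6.1 | Last visit before discontinuation | None |
| AE analysis | Protocol 7.3.3 | 7 days | None |
| On-treatment definition for AEs | SAP 6.1 | 7 days | None |
| AE data sources | SAP 7.8.1 | No cut-off visible for the merged data | None |

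Take a cancer with onset on day 8 after last intake, reported under Protocol 5.2.2.1 and held in the merged data. It is not treatment-emergent under Protocol 7.3.3 and not on treatment under SAP 6.1, and no readable table takes it in. The same cancer with onset on day 7 is tabulated.

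**How much could be lost.** The documents give no enrolment target, dropout rate or cancer rate, so the following is illustration only. Assumptions: a share d of patients stops, on average at 1.5 years; 3,000 complete 3 years; the 7-day tail is ignored; one constant background rate of 5, 10 or 15 cancers per 1,000 person-years applies on and off drug.

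- N = 3,000/(1 − d)
- On-treatment person-years = 3,000 × 3 + (N − 3,000) × 1.5
- Person-years after stopping, to 3 years = (N − 3,000) × 1.5

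| d | N | On-treatment PY | PY after stopping | Share after stopping | Late cancers at 5 / 10 / 15 per 1,000 |
|---|---|---|---|---|---|
| 10% | 3,333 | 9,500 | 500 | 5% | 2.5 / 5.0 / 7.5 |
| 30% | 4,286 | 10,929 | 1,929 | 15% | 9.6 / 19.3 / 28.9 |
| 50% | 6,000 | 13,500 | 4,500 | 25% | 22.5 / 45.0 / 67.5 |

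These are cancers that would arise. Only those actually reported can be lost at the analysis stage, and that number cannot be derived from the documents. Because the rate is held constant, the count falls but the on-treatment rate per person-year does not change.

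**What a comparison with national incidence could show.** Over 9,000 person-years (3,000 × 3) at the same assumed rates, the expected counts are 45 / 90 / 135. At an observed/expected ratio of 1, the exact Poisson 95% intervals are 0.73–1.34 / 0.80–1.23 / 0.84–1.18. A true ratio of about 1.48 / 1.32 / 1.26 is needed for 80% power (one-sided 0.025). All of this assumes that every cancer is captured. If only a share c is captured, the ratio estimates c times the true ratio: capture of 1/1.5 = 67% would make a true ratio of 1.5 read as 1.

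**The case against.** Four points deserve weight.

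- **The wording is softer than a hard stop.** Protocol 7.3.3 says analysis will concentrate on treatment-emergent events, and SAP 6.1 defines what is on treatment without saying that other events are discarded. SAP 7.8.1 also defers detail to a company standard that is not available here. This stands in part: exclusion is the natural reading of two matching 7-day rules with no visible table for later events, but it is an inference.
- **Text is missing where an exception would sit.** The item list in SAP 7.8.1, SAP 6.4 and other SAP sections cannot be read. A reader might infer that no expected count for malignancy is planned, so that an increase could never be judged. The documents do not allow that claim. None appears in the readable text, but the gaps could hold one. Exposure is also summarised under SAP 7.7, so an external comparison of on-treatment cancers stays possible.
- **Selective loss is not shown.** A reader might infer that patients who stop during a diagnostic work-up are the ones removed. The window runs on when the event occurs, the source data carry an onset date (Protocol 8.3.1), and nothing readable equates onset with diagnosis. Early symptoms could put onset inside the window. The illustration above, with its constant rate, does not test this either.
- **The gap starts before analysis.** Protocol 5.3.1 requires only ADRs and fatal events in the eCRF, so a non-fatal cancer judged unrelated may be missed even on treatment, although Protocol 5.2.2.1 and the visit tables in Protocol 6.2 point the other way. This stands. Widening the analysis window recovers nothing that was never reported, and an observed/expected ratio against complete national incidence would be biased low.

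**Conclusion.** The mismatch is real and should be corrected. On the readable text, cancers are reportable without time limit but analysed within a 7-day tail, so reported later cancers would be left out of the treatment-emergent tables and the malignancy count would be too low. The direction follows from the rules. The size is unknown: the 5% to 25% of person-time after stopping depends wholly on assumed discontinuation of 10% to 50% at a mean of 1.5 years, and says nothing about how many late cancers were reported.

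The conclusion rests on two assumptions: that no unreadable section already exempts cancer, and that the 7-day definitions govern the tables. It does not extend to saying that the study cannot address malignancy, or that the loss is selective. The study is single-arm and descriptive, so an observed/expected ratio is an option and its absence from the readable text is not in itself a fault.

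**What to change.** 1. In Protocol 7.3.3 and SAP 7.8.1, exempt malignancy from the 7-day limit. Tabulate all reported cancers, new or worsened, with onset after first intake, in two columns: up to 7 days after last intake, and later. Show on-treatment person-years beside the on-treatment count.
2. Footnote that the later column is a lower bound, because planned observation ends at discontinuation (Protocol 6.1).
3. Reconcile Protocol 5.2.2.1, 5.3.1 (collection and expedited reporting) and 6.1 on whether non-fatal cancers judged unrelated are collected, and for how long.
4. Optionally, add an observed/expected ratio for on-treatment cancers against national incidence, labelled descriptive. State that incomplete capture under Protocol 5.3.1 biases it low, so a ratio near or below 1 is not reassurance.

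Items 1 and 2 cost a few lines of text and one table built from events already reported and exposure already summarised. They need no new visits and leave the primary ADR analysis as it is. Item 3 needs a protocol clarification and cannot recover cancers that sites were never asked to record. Item 4 needs an outside source of age- and sex-specific incidence, chosen before the counts are seen.

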### **7.3.4 Interim analyses**

Interim analyses will be performed periodically for the purpose of creating safety update reports to the local authority as well as for publications.

## **7.4 HANDLING OF MISSING DATA**

The REML based MMRM analysis will handle missing data for continuous efficacy endpoints for patients who discontinue the study treatment prematurely or whom corresponding assessments / measurements are not documented / available.

## **7.5 RANDOMISATION**

No randomisation of patients for treatment is performed, since this is an observational study.

## **7.6 DETERMINATION OF SAMPLE SIZE**

According to the request from the Japanese authority, this PMS will target to include 3,000 patients who complete a 3-year JARDIANCE® observation period. There is no target number of enrolment. For the 3,000 completer patients, an ADR with a true incidence of at least 0.10% (or 0.16%) will occur in at least one patient with a probability of 95% (or 99%).

In addition, according to the request from the Japanese authority, this PMS will target to include elderly patients, patients with renal dysfunction and hepatic dysfunction. The sample size for this patient subset was determined based on the following:

Elderly patients ( $\geq 75$  years)

Elderly patients were observed in 14.6% of the patients with type 2 diabetes mellitus based on the National Health and Nutrition Examination Survey (2007) [R13-5199]; it is estimated that approximately 400 ~ 500 elderly patients will be included in the 3,000 completer patients.

Based on this assumption, more than 100 elderly patients are highly likely to be enrolled in this PMS.

#### Renal dysfunction

The patients with renal dysfunction (eGFR 45~60 mL/min/1.73m^2) were observed in 14.8% of the patients with type 2 diabetes mellitus in based on the historical cohort study with type 2 diabetes [R13-5102]; it is estimated that approximately 400 ~ 500 patients with renal dysfunction will be included in the 3,000 completer patients.

Based on this assumption, 100 patients with renal dysfunction are highly likely to be enrolled in this PMS.

#### Hepatic dysfunction

Based on the result that hepatic function disorder was observed in 13.7% of the patients in the surveillance on the long-term use of Amaryl® Tablets, an agent for type 2 diabetes [R11-4205], it is estimated that approximately 350 ~ 450 patients with hepatic dysfunction will be included in the 3,000 completer patients.

Based on this assumption, 100 patients with hepatic dysfunction are highly likely to be enrolled in this PMS.

If the number of completer patients with 3-year JARDIANCE® observation period or specific diseases is less than expected by monitoring received CRF data, registration period or total number of enrolled patients may be extended.

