**3.3 SELECTION OF POPULATION**

Total number of entered patients is 3,000 patients with the assessment of 3-year completed administration.

No limitations are set up on background factors of patients and their concomitant drugs in use of actual medical practice.

Estimated number of enrolled patients with renal dysfunction ( $45 \text{ mL/min/1.73m}^2 \leq \text{eGFR} < 60 \text{ mL/min/1.73m}^2$ ) is 100.

Grades for renal dysfunction are as follows.

Normal:  $\text{eGFR} \geq 90 \text{ mL/min/1.73m}^2$   
Mild:  $\text{eGFR} \geq 60 \text{ mL/min/1.73m}^2$  and  $< 90 \text{ mL/min/1.73m}^2$   
Moderate:  $\text{eGFR} \geq 30 \text{ mL/min/1.73m}^2$  and  $< 60 \text{ mL/min/1.73m}^2$   
Severe:  $\text{eGFR} < 30 \text{ mL/min/1.73m}^2$

Estimated number of enrolled elderly patients ( $\geq 75$  years) is 100.

Estimated number of enrolled patients with hepatic dysfunction is 100.

Patients with hepatic dysfunction: Investigator judgment is moderate or severe.

Investigator should judge the grade for hepatic dysfunction by using lab data category as described below and symptoms/concomitant diagnoses.

Normal: Normal AST/ALT  
Mild: AST/ALT >ULN and <3x ULN  
Moderate: AST/ALT ≥3xULN and <5x ULN + total Bil ≤ 2xULN  
Severe: AST/ALT ≥5 xULN, or AST/ALT ≥3xULN and <5x ULN + total Bil > 2xULN  
ULN is taken from the corporate standard reference range (001-MCG-157\_RD-01: Standard Ranges).

Sites throughout entire country will be equally listed according the size of the hospitals or general clinics at which JARDIANCE® Tablets are available for prescription.

Expected number of patients per site is 5-30 patients. Patients will be selected by using the continuous investigation system. The continuous investigation system is commonly used in Japanese PMS and accepted as a patient selection process by the PMDA.

Continuous investigation system is a method of registration that the investigator enrolls the patients who will start administration of marketed product into the PMS continuously (without exception) until the requested number of patients is reached.

Preferably, investigators will register patients within 14 days including the day on which the administration of JARDIANCE® Tablets is started. However, patients who are registered over 15 days after starting administration of JARDIANCE® Tablets are also used for safety and efficacy analysis.

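### Is the hepatic-dysfunction projection in protocol section 7.6 undermined by a prevalence whose grade is not stated?

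*Protocol*

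**What the plan says.** Protocol section 7.6 sets the overall size by completers: "this PMS will target to include 3,000 patients who complete a 3-year" observation period. It adds: "There is no target number of enrolment". For the hepatic subgroup it reports that "hepatic function disorder was observed in 13.7% of the patients in the surveillance on the long-term use of" another antidiabetic product. From this it derives the projection: "it is estimated that approximately 350 ~ 450 patients with hepatic dysfunction will be included in the 3,000 completer patients". On that stated assumption it regards 100 enrolled hepatic patients as very probable.

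Protocol section 3.3 gives the figure to be met, "Estimated number of enrolled patients with hepatic dysfunction is 100", and the definition: "Patients with hepatic dysfunction: Investigator judgment is moderate or severe". Transaminases above normal but below three times the upper limit are graded mild, so patients judged mild do not count.

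The renal paragraph of section 7.6 has the same form but states its criterion with the prevalence: "The patients with renal dysfunction (eGFR 45~60" mL/min/1.73 m²) make up 14.8% of its source, and "it is estimated that approximately 400 ~ 500 patients with renal dysfunction will be included in the 3,000 completer patients". That is the eGFR band named in section 3.3. The elderly paragraph likewise uses 75 years or older in both places.

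**The concern.** Of the three subgroup projections, only the hepatic one applies a prevalence with no stated criterion to a subgroup that has a restrictive one. If the 13.7% includes mild cases, the number meeting section 3.3 is smaller than 411, possibly much smaller, and the confidence about reaching 100 would rest on a mismatch. The subgroup is there at the authority's request and the results go into a re-examination dossier. A reader could then compare the achieved moderate/severe count with 350 to 450, which may be the wrong benchmark, or find that a requested subgroup is too small to describe.

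**Working it through.** **Inputs**
- Prevalence 13.7%, 3,000 completers, projection 350 to 450: protocol section 7.6.
- Expected 100 enrolled, moderate or severe only: protocol section 3.3.
- 1,300 sites: protocol synopsis. Expected 5 to 30 patients per site: protocol section 3.3.
- Moderate/severe share *f* of the 13.7%: not in the documents, so it is varied as an assumption.

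**Step 1: the plan's own figure.** Expected count = 3,000 × 0.137 = 411. The binomial SD is √(3,000 × 0.137 × 0.863) = 18.8, so a 95% range is about 374 to 448. The stated 350 to 450 is reproduced. If the whole 13.7% were moderate or severe, the chance of at least 100 is practically 1.

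**Step 2: how many enrolled?** The 100 is a count of enrolled patients, while the projection is among completers. With any dropout, more than 3,000 must be enrolled. There is no enrolment target, but the planning inputs give a scale: 1,300 × 5 = 6,500 and 1,300 × 30 = 39,000. These products are not a stated target. They do show that 3,000 enrolled is the least favourable case, since it requires every patient to complete three years.

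**Step 3: the share needed.** For *N* enrolled, the count is taken as Binomial(*N*, 0.137 × *f*). The expected count reaches 100 at *f* = 100 / (0.137 × *N*). The 95% column gives the *f* at which P(at least 100) = 0.95.

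| Enrolled *N* | *f* for an expected 100 | *f* for 95% chance | Moderate/severe prevalence at 95% |
|---|---|---|---|
| 3,000 | 24.3% | 28.4% | 3.9% |
| 4,000 | 18.2% | 21.3% | 2.9% |
| 5,000 | 14.6% | 17.0% | 2.3% |
| 6,500 | 11.2% | 13.1% | 1.8% |
| 10,000 | 7.3% | 8.5% | 1.2% |

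**Step 4: chance of at least 100 for assumed shares.**

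| *f* | *N* = 3,000 | *N* = 5,000 | *N* = 6,500 |
|---|---|---|---|
| 15% | <0.001 | 0.62 | 0.999 |
| 20% | 0.03 | >0.999 | >0.999 |
| 25% | 0.62 | >0.999 | >0.999 |
| 30% | 0.99 | >0.999 | >0.999 |

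From *f* = 30% upward, every enrolment size shown gives about 99% or more. The poor probabilities occur where a low share meets an enrolment well below what the site figures imply.

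**Step 5: what depends on it.** Protocol section 7.2 says the analyses are descriptive and exploratory, with no formal tests. Section 7.6 provides for monitoring the received data and for extending registration or enrolment if numbers run short. SAP Table 6.2: 1 (code G1.4) gives the end of registration as 31 May 2017, and the SAP is dated 22 October 2020. Hepatic grade is recorded at baseline (protocol sections 5.4.1 and 6.2.1), and SAP sections 6.3 and 7.1 plan descriptive baseline tables on the safety set.

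**The case for a change.** The strongest argument for a change is that the condition that matters is hidden. Section 7.6 makes its conclusion depend on an assumption, but the assumption it names is the 13.7%, not the grade. The renal and elderly paragraphs show that stating a matching criterion was feasible. The extension clause is permissive and does not say whether a shortfall is judged against 350 to 450 completers or 100 enrolled. A note on the grade, with the achieved moderate/severe count set against 100, would cost almost nothing.

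The factual part stands: the grade is unstated, and the documents do not link the two definitions. At a share below about 13%, 100 would not be assured even with 6,500 enrolled.

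The case for acting does not stand. The definition behind the 13.7% belongs to a cited source outside these documents, so a mismatch is possible but not shown. Investigators grade on symptoms and diagnoses as well as laboratory categories, so the transaminase cut-offs alone do not fix the share. The ambiguity in the extension clause applies equally to the renal subgroup and can no longer affect enrolment. The count itself may already be in the baseline tables. SAP section 6.4, to which section 7.4.2 refers for subgroup analysis, is not visible, so the count cannot be called missing.

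**Conclusion.** The observation is correct but does not call for a change. Section 7.6 leaves out the grade behind its hepatic prevalence, so 350 to 450 is undocumented for the subgroup defined in section 3.3. It is not shown to be wrong, and 100 is not shown to be out of reach. The 100 sits against a projection of 411, roughly a fourfold margin. The share needed for 95% assurance falls from about 28% in the least favourable case (3,000 enrolled, no dropout) to about 13% at 6,500 and 8.5% at 10,000.

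These figures assume that the 13.7% carries over to this population, that counts are binomial, and that enrolment is of the order the site figures suggest. The true share is unknown. With recruitment closed, descriptive analyses, and no visible result that depends on the subgroup reaching 100, rewriting the projection would alter neither the data nor any planned analysis. Analysts can tabulate the moderate/severe count from the recorded grade and read it against the 100 in section 3.3.
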